5.1 Inclusion criteria

Participants eligible for inclusion in this study must meet **all** of the following criteria:

- 1. Signed informed consent must be obtained prior to participation in the study
- 2. Age \geq 18 years at the date of signing the informed consent form (ICF)
- 3. Morphologically confirmed diagnosis of myelodysplastic syndrome (MDS) based on 2016 WHO classification (Arber et al, 2016) by local investigator assessment with one of the following Prognostic Risk Categories, based on the revised International Prognostic Scoring System (IPSS-R) (Greenberg et al 2012):
 - Very high (> 6 points)
 - High (> 4.5-6 points)
- 4. Not immediately eligible for hematopoietic stem-cell transplantation (HSCT) or intensive chemotherapy at the time of screening due to individual clinical factors such as age, comorbidities and performance status, donor availability (de Witte et al 2017)
- 5. Eastern Cooperative Oncology Group (ECOG) performance status of 0, 1 or 2
- 6. Indication for azacitidine treatment according to the investigator, based on local standard medical practice and institutional guidelines for treatment decisions

- 7. AST and ALT \leq 3 × upper limit of normal (ULN)
- 8. Total bilirubin $\leq 1.5 \times$ ULN (except in the setting of isolated Gilbert syndrome, where participants may only be included with total bilirubin $\leq 3.0 \text{ x ULN}$)
- 9. Estimated Glomerular Filtration Rate (eGFR) ≥ 30 mL/min/1.73 m² (estimation based on Modification of Diet in Renal Disease) (MDRD) formula, by local laboratory)
- 10. Participant is able to communicate with the investigator, and has the ability to comply with the requirements of the study procedures

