8.3 Efficacy

8.3.1 Efficacy assessments

Disease response will be assessed locally by the investigator in all participants (MDS) according to modified IWG for MDS and WHO criteria (Cheson et al 2000, Cheson et al 2006, Arber et al, 2016, Platzbecker 2019). Response criteria are described in Table 8-2.

Investigators will assess and document response/progression at each time point as per the visit schedule. For efficacy analyses, baseline assessment is defined as the last non-missing assessment on or before the date of sabatolimab.

In addition, the hematological improvement per modified IWG-MDS criteria (Cheson et al 2006) will be assessed in all enrolled participants to report specific hematologic improvement (HI) of cytopenias in the three hematopoietic lineages: erythroid (HI-E), platelet (HI-P), and neutrophil (HI-N).

Response category	Definition [#]
Complete remission (CR)	Bone marrow:
	<= 5% blasts with normal maturation of all cell lineages. (Note: Persistence of dysplasia will be noted but does not preclude achievement of complete remission [CR])
	Peripheral blood:
	1. Hgb $\geq 10 \text{ g/dl}$ AND
	2. Platelets $\geq 100*10^9$ /L AND
	3. Neutrophils $\geq 1.0*10^9$ /L AND
	4. Blasts 0%
	(Note: the participant must not receive RBC or platelet transfusions, myeloid growth factor within 2 weeks before this disease assessment)
marrow Complete remission (mCR)	Bone marrow:

Table 8-2Modified response classification per IWG-MDS criteria (Platzbecker et
al 2019, Cheson et al 2006, Cheson et al 2000)

Response category	Definition [#]
	<= 5% blasts and blast count decrease by \geq 50% compared to baseline
	Peripheral blood/transfusion: Marrow CR may be achieved with or without improved blood counts or with or without transfusions
Partial remission (PR)	All CR criteria except
	Bone marrow: $\geq 50\%$ decrease from baseline in blasts in bone marrow AND blast count in bone marrow $> 5\%$
Stable Disease (SD)	Failure to achieve at least PR, but no evidence of progression for >8 weeks
Relapse from CR	Only in participants with a CR
	At least 1 of the following criteria is met: [in absence of another explanation not due to MDS, such as acute infection, bleeding, hemolysis, etc. Note that observation of peripheral blasts is not a sufficient criterion for relapse. However in that case, a bone marrow examination should be made to determine whether relapse has occurred]
	1. Return to baseline bone marrow blast percentage

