	2. Decrease of $\geq 50\%$ from maximum remission/response*** levels in neutrophils AND neutrophils $<1.0*10^{9}/L$. Note: neutrophils counts during periods of active infection will not be considered in determining the maximum
	3. Decrease of \geq 50% from maximum remission/response*** levels in platelets AND platelets < $100*10^{9}/L$
	4. Decrease from maximum remission/response*** levels in Hgb concentration by ≥ 1.5 g/dL AND Hgb < 10 g/dL
	5. Becoming transfusion dependent**
Disease progression	At least 1 of the following criteria is met:

Response category	Definition [#]
	[in absence of another explanation not due to MDS, such as acute infection, bleeding, hemolysis, etc. Note that observation of peripheral blasts is not a sufficient criterion for progression. However in that case, a bone marrow examination should be made to determine whether relapse has occurred]
	Bone marrow according to the number of blasts of the participant at baseline:
	1. Less than 5% blasts at baseline : \geq 50% increase in blasts over baseline to > 5% blasts
	2. 5% - < 10% blasts at baseline : \geq 50% increase over baseline to > 10% blasts
	3. $10\% - < 20\%$ blasts at baseline : $\ge 50\%$ increase over baseline to $> 20\%$ blasts.
	Participants with more than 20% of blasts will be considered to have transformation to acute leukemia per 2016 WHO classification (Arber et al, 2016)
	Peripheral blood:
	1. Decrease of $\geq 50\%$ from maximum remission/response*** levels in neutrophils AND neutrophils < $1.0*10^9/L$. Note: neutrophils counts during periods of active infection will not be considered in determining the maximum
	2. Decrease of \geq 50% from maximum remission/response*** levels in platelets AND platelets < $100*10^9/L$
	3.Reductionfrommaximumremission/response***levelsinHgbby2g/dLANDHgb $10g/dL$
	Becoming transfusion dependent**
	Occurrence of acute leukemia, or extramedullary leukemia per investigator's judgement

Modified Hematologic Improvement per IWG-MDS criteria (Cheson et al 2006)

Response category	Definition [#]
HI category	Definition [#] (HI must last at least 8 weeks)
Erythroid response (HI-E) (pretreatment*, <11 g/dL)	1. Hgb increase from baseline by \geq 1.5 g/dL, in at least 2 consecutive Hgb measurements and maintained over at least 8 weeks

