2.5.1.2 Cohort 2 of Safety run-in (Part 1) and Expansion (Part 2)

The primary endpoint is the proportion of participants included in the FAS and assigned to sabatolimab at the 800 mg Q4W dose level (in both safety run-in and expansion parts) who achieved a complete remission (CR) as per investigator assessment.

Response assessment rules

Response assessment will be performed by the investigator according to the assessment schedule depicted in protocol Table 8-1 based on available bone marrow assessment (C3D1, C7D1, C10D1, C13D1 and then C19D1, C25D1 and then every 12 cycles), hematology data (at D1, D8, D22 of the first 2 cycles and then D1 and D8 of each cycle until end of treatment and then every 12 weeks) and all transfusions records as detailed in s using the modified version of the published response criteria IWG for MDS. Moreover, response assessments can be performed at any time if clinically indicated, e.g. for confirmation of response but also for any suspicion of progression/relapse. These assessments are recorded as an unscheduled visit in the eCRFs and will be considered for the overall determination of response and progression/relapse with the respective assessment date.

The investigator does not determine best overall response, he/she is assessing only the response based on the given bone marrow and peripheral blood data, the history of transfusions and myeloid growth factor received within the last 2 weeks.

The best overall response (BOR) will be derived based on the CR primary endpoint rules by Novartis as below:

- CR = at least one determination of CR without progression or relapse from CR within the four weeks after CR
- mCR = at least one determination of mCR (and not qualifying for a CR).
- PR = at least one determination of PR (and not qualifying for a CR, mCR).
- HI = at least one determination of HI (and not qualifying for a CR, mCR, PR)
- SD = at least one SD assessment and not qualifying for CR, mCR, PR or HI).
- PD = progression after start of treatment and not qualifying for CR, mCR, PR, HI or SD.
- UNK = all other cases (i.e., not qualifying for confirmed CR or mCR or PR or HI and without SD or progression).

Details for the definition of response categories (captured in the eCRF by the Investigator) as defined in Table 8-2 of the protocol, are described in Table 2-2 below.

Response category	Definition [#]	
Complete remission (CR)	Bone marrow:	

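### Relapse criterion 1 sets no absolute marrow blast level, so a participant who entered with blasts of 5% or less can meet CR and relapse from CR on the same later marrow

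*Protocol*

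**What the plan says.** The response definitions are in protocol section 8.3.1, Table 8-2, and are repeated in SAP section 2.5.1.2, Table 2-2.

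- **CR, marrow part:** "<= 5% blasts with normal maturation of all cell lineages". Hemoglobin, platelet, neutrophil and peripheral-blast limits also apply. No fall in marrow blasts from baseline is required.
- **mCR, marrow part:** "<= 5% blasts and blast count decrease by" at least 50% from baseline. Here a fall is required.
- **Relapse from CR:** it applies "Only in participants with a CR" and is declared when "At least 1 of the following criteria is met". Criterion 1 is "Return to baseline bone marrow blast percentage". Criteria 2, 3 and 4 combine a fall from the best value with an absolute limit: neutrophils below 1.0, platelets below 100 (both x10^9/L) and hemoglobin below 10 g/dL. Criterion 5 is becoming transfusion dependent.
- **Progression, marrow part:** there is a stratum for baseline "Less than 5% blasts", which requires a rise of at least 50% to a value above 5%.

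Inclusion criterion 3 (protocol section 5.1) is an IPSS-R score, for example "High (> 4.5-6 points", with no minimum blast percentage. SAP section 2.5.1.2 derives best overall response with the rule "CR = at least one determination of CR without progression or relapse from CR within the four weeks after CR".

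**The concern.** Relapse should mean that the participant has left remission. For someone who entered with 5% blasts or less, the baseline value lies inside the CR range, so going back to it does not take the marrow out of that range. The protocol expects such entrants: eligibility sets no blast minimum, and the progression section has a stratum for them.

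Relapse is an event for duration of CR, duration of CR/mCR, duration of response, PFS and EFS (protocol section 12.5.1.2; SAP section 2.6.1.2). A relapse declared while the marrow and counts still meet CR would enter all five as a failure and shorten them. SAP section 2.6.1.2 still has every time-to-event endpoint derived and listed with its event type, so the definition remains in use although the expansion was not opened.

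**Working it through.** The plan gives no figure for this point, so the check is of the definitions, followed by an illustration on assumed inputs.

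**1. One participant, three marrows**

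| Time | Marrow blasts | Counts | CR marrow limit (<=5%) | Criterion 1 (back to baseline) |
|---|---|---|---|---|
| Screening | 4% | low | – | – |
| C3D1 | 2% | recovered | met: CR | no |
| C7D1 | 4% | recovered | met: CR | met: relapse |

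At C7D1 criteria 2 to 4 are not met, because the counts are still in the CR range. The low-blast progression row is not met either, because 4% is not above 5%. Criterion 1 alone produces the relapse.

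**2. Extent of the overlap**

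Take whole-number baseline blasts b from 0 to 19% and on-study blasts m from 0 to 20%. Count the pairs with m <= 5 (CR marrow limit) and m >= b (at or back to baseline).

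- As written: 21 pairs, all with b <= 5.
- A return needs an earlier fall below baseline, which is impossible at b = 0. Removing those 6 pairs leaves 21 - 6 = 15, with b from 1 to 5.
- With m > 5 added to criterion 1: 0 pairs.
- Progression marrow rows as written, against the CR limit: 0 pairs.

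The overlap is therefore specific to relapse criterion 1, and a floor at the CR limit removes it.

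**3. Can it reach the CR rate?**

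Scheduled marrows are at C3D1, C7D1, C10D1 and C13D1, then further apart (protocol section 8.3.1). The gaps are 4 x 28 = 112 days (16 weeks) and 3 x 28 = 84 days (12 weeks). With a window of 7 days either side, the shortest scheduled gap is 84 - 14 = 70 days. The four-week rule for best overall response cannot be triggered by two scheduled marrows. Only an unscheduled or end-of-treatment marrow within four weeks of CR could do it through criterion 1.

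**4. How easily could a reading return to baseline? (illustration)**

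Assumptions, none from the documents: baseline reading 4%, a differential of 200 or 500 cells, constant true blasts p during CR, independent readings, and mechanical use of criterion 1. The per-marrow probability q of a reading at or above 4% is P(X >= 8), X ~ Bin(200, p), or P(X >= 20), X ~ Bin(500, p). Over three marrows it is 1 - (1 - q)^3.

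| True blasts in CR | Cells | q per marrow | Over three marrows |
|---|---|---|---|
| 3% | 200 | 0.254 | 0.585 |
| 3% | 500 | 0.121 | 0.322 |
| 2% | 200 | 0.049 | 0.141 |
| 2% | 500 | 0.003 | 0.009 |

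The result depends heavily on how far below baseline the true value has fallen.

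**The case against.** The strongest reply is that criterion 1 says return, that it applies only after CR, and that the investigator makes the call. Several parts of this stand.

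- **Unchanged marrow.** A reader might infer that a participant at 4% at baseline and 4% at the first CR marrow is in CR and relapse at once. The wording does not support this: a value that never fell has not returned. Only the fall-and-return path is a clear conflict.
- **Investigator judgment.** Response categories are recorded by the investigator, and the sponsor derives only best overall response. Someone seeing 4% blasts with recovered counts may well record continuing CR. The probabilities above are therefore not rates of recorded relapse. But the text then gives two answers for the same marrow, and classification may differ between sites.
- **The exclusion for explanations not due to MDS.** Its list is open-ended, and counting error could arguably be brought under it. It still sets no blast level, and its examples are infection, bleeding and hemolysis.
- **Primary endpoint and power.** A reader might infer that the CR rate, or the 36-of-70 success rule, is materially eroded. The documents do not support this. The route is limited to unscheduled or end-of-treatment marrows, the share of low-blast entrants is not given, and the SAP drops the primary CR analysis.
- **Breadth.** Not every participant with low baseline blasts is affected. He or she must reach CR, fall below baseline, return while still at 5% or less, and be recorded as relapsed.
- **Scale and wording.** The 800 mg cohort was planned at about 12, and Kaplan-Meier output depends on available follow-up and events. Italics in Table 8-2 mark the sponsor's changes to the published criteria; criterion 1 shows none in the extracted text, so a floor would probably be one more modification.

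**Conclusion.** The definitions conflict in a narrow but clear case: entry with blasts of 5% or less, CR with blasts below baseline, then a return to baseline with counts still recovered. Criterion 1 is the only blast or count criterion for relapse without an absolute limit, and the table's own low-blast progression row has one. The likely direction of error is false relapse events and shorter duration of CR, duration of CR/mCR, duration of response, PFS and EFS. Any effect on the CR rate is confined to an unscheduled or end-of-treatment marrow within four weeks of CR.

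The size cannot be stated. The documents give neither the share entering at 5% or less nor the number of cells counted, and the counting-error figures hold only under the stated assumptions. In a cohort planned at about 12, one misclassified relapse would be visible in the listings and in any median. The point deserves correction, but it does not undermine the trial's main results.

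**What to change.** **Definition.** In protocol Table 8-2 and SAP Table 2-2, reconcile criterion 1 with CR by requiring return to the baseline blast percentage and marrow blasts above 5%, for endpoint classification.

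**Abbreviated CSR.** Keep the investigator-assessed relapse as the primary record. Using the marrow blast percentages that SAP section 2.6.1.2 already lists, flag any criterion-1 relapse with blasts of 5% or less. For those participants, also report duration of CR, duration of CR/mCR, duration of response, PFS, EFS and best overall response with the floor applied, beside the investigator-based result. If no case is flagged, one sentence saying so closes the point.

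**Cost.** One clause in two tables and a check on data already collected. Changing the protocol table needs an amendment; the CSR step needs only the SAP. A few relapses would be dated later, once blasts exceed 5% or another criterion is met, and the table would carry one more sponsor modification.

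**Boundary.** Protocol section 6.1.5 also names relapse among the reasons for stopping study treatment. The sponsor must reconcile that passage with the definition separately; no treatment rule is proposed here.

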	2. Relevant reduction from baseline of units of RBC transfusions by an absolute number of at least 4 RBC transfusions/8 weeks compared with the pre-treatment transfusion number in the previous 8 weeks. Only RBC transfusions given for a Hgb of < 9 g/dL pre- treatment will count in the RBC transfusion response evaluation.
Platelet response (HI-P) (pretreatment*, <100 x 10 ⁹ /L)	1. Absolute increase from baseline of \geq 30 x 10 ⁹ /L for participants starting with $>$ 20 x 10 ⁹ /L platelets
	2. Increase from baseline from $< 20 \times 10^9$ /L to $> 20 \times 10^9$ /L and by at least 100% for participants starting with $< 20 \times 10^9$ /L platelets
Neutrophil response (HI-N) (pretreatment*, <1.0 x 10 ⁹ /L)	At least 100% increase and an absolute increase from baseline of $> 0.5 \text{ x } 10^9/\text{L}$

[#]If not defined otherwise, all of the criteria apply. Words that are written in italics highlights the modifications from the IWG criteria described in the reference publications.

**Pretreatment counts correspond to the baseline (not influenced by transfusions)*

**Definition of transfusion dependence and independence for red blood cells (RBC) and/or platelets are described below.

***maximum remission/response levels correspond to the best values reported in post baseline.

Transfusions Status Definitions for RBC/platelets

Transfusions for intercurrent diseases not due to study indication (e.g. bleeding, surgical procedure, hemolysis, infections) should not be taken into account for the following:

Transfusion dependence:

1. At baseline: participants having received ≥ 3 units of transfusion within the 8 consecutive
weekspriortobaseline.2. Post-baseline: participants having received ≥ 3 units of transfusion within any 8 consecutive
weeks during the course of the study ≥ 3 units of transfusion within any 8 consecutive

Transfusion independence:

1. At baseline: participants having received 0 units of transfusion within the 8 consecutive weeks prior to baseline.

2. Post-baseline: participants having received 0 units of transfusion within any 8 consecutive weeks during the course of the study.

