	1. Less than 5% blasts at baseline : \geq 50% increase in blasts over baseline to > 5% blasts	
	2. 5% - < 10% blasts at baseline : \geq 50% increase over baseline to > 10% blasts	
	3. 10% - < 20% blasts at baseline : \geq 50% increase over baseline to > 20% blasts.	
	Participants with more than 20% of blasts will be considered to have transformation to acute leukemia per 2016 WHO classification (Arber et al, 2016)	
	Peripheral blood:	
	1. Decrease of \geq 50% from maximum remission/response*** levels in neutrophils	

AND neutrophils $< 1.0*10^{9}/L$. Note: neutrophils counts during periods of active infection will not be considered in determining the maximum
2. Decrease of \geq 50% from maximum remission/response*** levels in platelets AND platelets < $100*10^{9}/L$
3. Reduction from maximum remission/response *** levels in Hgb by $\geq 2g/dL \text{ AND } Hgb < 10g/dL$
Becoming transfusion dependent**
Occurrence of acute leukemia, or extramedullary leukemia per investigator's judgement

Modified Hematologic Improvement per IWG-MDS criteria (Cheson et al 2006)

HI category	Definition [#] (HI must last at least 8 weeks)	
Erythroid response (HI-E) (pretreatment*, <11 g/dL)	1. Hgb increase from baseline by \geq 1.5 g/dL, in at least 2 consecutive Hgb measurements and maintained over at least 8 weeks	
	2. Relevant reduction from baseline of units of RBC transfusions by an absolute number of at least 4 RBC transfusions/8 weeks compared with the pre-treatment transfusion number in the previous 8 weeks. Only RBC transfusions given for a Hgb of < 9 g/dL pre- treatment will count in the RBC transfusion response evaluation.	
Platelet response (HI-P) (pretreatment*, <100 x 10 ⁹ /L)	1. Absolute increase from baseline of \geq 30 x 10 ⁹ /L for participants starting with $>$ 20 x 10 ⁹ /L platelets	
	2. Increase from baseline from $< 20 \times 10^9/L$ to $> 20 \times 10^9/L$ and by at least 100% for participants starting with $< 20 \times 10^9/L$ platelets	
Neutrophil response (HI-N) (pretreatment*, <1.0 x 10 ⁹ /L)	At least 100% increase and an absolute increase from baseline of $> 0.5 \times 10^9/L$	
[#] If not defined otherwise, all of the criteria ap	ply. Words that are written in italics highlights	

"If not defined otherwise, all of the criteria apply. Words that are written in italics highlights the modifications from the IWG criteria described in the reference publications.

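### As written, Table 8-2 and SAP Table 2-2 require both HI-E criteria, which shuts out participants with fewer than 4 qualifying RBC transfusions and could lower ORR

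*Protocol*

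**What the plan says.** Disease response, including hematologic improvement (HI), is assessed by the investigator against protocol Table 8-2 (Section 8.3.1), which SAP Table 2-2 (Section 2.5.1.2) reproduces. The column heading of the HI block carries the footnote mark #. In the protocol that footnote reads "If not defined otherwise, all of the criteria apply". The SAP carries the same footnote ("If not defined otherwise, all of the criteria ap…").

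The HI-E row is open to participants with pretreatment Hgb below 11 g/dL and has two numbered items:

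- Item 1: a Hgb rise from baseline of at least 1.5 g/dL, "in at least 2 consecutive Hgb measurements and maintained over at least 8 weeks".
- Item 2: "Relevant reduction from baseline of units of RBC transfusions by an absolute number of at least 4 RBC transfusions/8 weeks", compared with the 8 weeks before treatment. On what counts, the row says: "Only RBC transfusions given for a Hgb of < 9 g/dL" pre-treatment.

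No connecting word stands between the items. Other rows do mark how their items combine. Relapse and progression are headed "At least 1 of the following criteria is met". The two HI-P items apply to different starting platelet counts (for example "and by at least 100% for participants starting with" a low count). HI-N is one sentence whose two conditions are joined by a conjunction.

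HI feeds two secondary endpoints. ORR counts a best response of HI or better (protocol Section 12.5.1; SAP Section 2.6.1). Duration of response runs from the first CR, mCR, PR or HI.

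**The concern.** HI-E is the only HI row with two numbered items and neither an either/or rule nor a split by subgroup. The footnote therefore governs it, and both items are required. That does not fit the row's own entry condition, which is a hemoglobin level with no transfusion requirement, or the instruction in Section 8.3.1 to assess HI in all enrolled participants. An anemic participant who is not transfused enters the row but can never respond.

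ORR and duration of response are at stake. The recruitment halt does not remove them: SAP Section 1.2 drops only the fatigue evaluation and keeps the other objectives, and Section 3 adds only the primary CR analysis to the list of analyses not performed. If investigators follow the footnote, ORR depends in part on how heavily participants were transfused at baseline. If they assume either item is enough, the reported ORR does not follow its written definition. If sites differ, ORR mixes two definitions. A stricter HI-E also removes some participants from the duration-of-response analysis and can delay the start of the clock for someone who shows erythroid improvement first and a deeper response later.

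**Working it through.** **1. Who can meet both items.** Let u be the number of qualifying RBC transfusions (given for Hgb below 9 g/dL) in the 8 weeks before treatment. I count one unit as one transfusion, since item 2 uses both words. The largest possible reduction is u, so item 2 needs u ≥ 4.

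| u | Largest cut | HI-E possible if both items needed | HI-E possible if one is enough |
|---|---|---|---|
| 0 | 0 | no | yes, by Hgb |
| 1 | 1 | no | yes, by Hgb |
| 2 | 2 | no | yes, by Hgb |
| 3 | 3 | no | yes, by Hgb |
| 4 or more | 4 or more | yes, if Hgb also rises ≥ 1.5 g/dL | yes, by either |

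The row u = 3 matters because Section 8.3.1 defines baseline transfusion dependence as at least 3 units in 8 weeks. Transfusions given at Hgb of 9 g/dL or above do not count, so some participants with 4 or more in total also fall in the upper rows.

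**2. Three cases under the literal rule.**

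- Untransfused, Hgb rises from 9 to 12 g/dL: item 1 is met (+3), the cut is 0, not HI-E.
- From 3 units to 0: the cut is 3, below 4, so not HI-E whatever Hgb does.
- From 6 units to 0 with Hgb stable at 8.5 g/dL: item 2 is met (cut 6), item 1 is not, not HI-E.

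**3. Direction.** Everyone who meets both items meets at least one. ORR under the both-items rule can therefore only equal or fall below ORR under the either-item rule.

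**4. Size.** The documents assume no ORR for this trial. The only breakdown they give for sabatolimab is the earlier study with an HMA (protocol Section 4.6): 35 evaluable participants, with 8 CR, 8 marrow CR and 6 stable disease with HI.

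- Stated ORR reproduced: (8 + 8 + 6)/35 = 22/35 = 62.9%.
- Without the HI-only responders: 16/35 = 45.7%.
- HI-only share: 6/35 = 17.1%.

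Let e be the fraction of HI-only responders who qualify through HI-E alone, and f the fraction of those lost under the both-items rule. The loss in points is 17.1 × e × f. Neither e nor f is given.

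| e | f | Loss in ORR (points) | Participants of 12 |
|---|---|---|---|
| 0 | any | 0 | 0 |
| 0.5 | 0.5 | 4.3 | 0.5 |
| 0.5 | 1 | 8.6 | 1.0 |
| 1 | 1 | 17.1 | 2.1 |

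In the 800 mg safety run-in cohort, planned at about 12, one participant is 1/12 = 8.3 points.

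**5. Primary endpoint.** The CR definition uses blasts and blood counts and does not use HI, so the CR rate does not change.

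**The case against.** The best counter-argument is that the table gives mixed signals. Where it wants conditions to hold together it usually says so: the CR, PR and HI-N rows contain an explicit conjunction and HI-E does not. Item 2 also speaks of transfusion response as an evaluation of its own. An investigator might well read the items as alternatives. These cues suggest that requiring both was not intended, but they do not override a footnote that says what to do when a row is silent.

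Other parts of the objection stand and limit the point. A reader might infer that ORR is understated. The documents do not show this. It would need investigators to apply the footnote literally to HI-E, and the affected participants to have no CR, mCR or PR (HI counts in best response only then, SAP Section 2.5.1.2) and no HI-P or HI-N. It would also need the either-item rule to be the intended one, which is nowhere stated; the criteria are labelled as modified.

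A reader might also infer that ORR here cannot be compared with the 62.9% of the earlier study. Section 4.6 does not say which HI-E rule that study used, so this is unsupported too. Nor is 17.1 points an estimate: Section 4.6 gives neither lineage nor transfusion history for the 6 HI-only responders.

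**Conclusion.** The point holds as a defect in a written rule. In both documents the footnote makes the two HI-E items cumulative. Followed literally, HI-E is unreachable with fewer than 4 qualifying RBC transfusions before treatment, and is denied to those who become transfusion free without a 1.5 g/dL rise in Hgb.

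The effect on ORR is possible, not demonstrated. It can only be downward or nil, and is 0 to 17.1 points if the earlier study's HI-only share of 6/35 is assumed to carry over. That study used a different regimen, and the top of the range needs every HI-only response to be erythroid alone and every one to be lost. The consequence is confined to ORR and duration of response, reported descriptively from small run-in cohorts because the expansion part will not open. The correction is still worth making: those endpoints will be reported, and one reclassified participant is visible in a cohort of about 12.

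**What to change.** In SAP Table 2-2 and protocol Table 8-2, head the HI-E cell with the phrase the relapse and progression rows already use, "At least 1 of the following criteria is met". Alternatively, assign each item to a baseline transfusion status, as HI-P assigns its items by platelet count. If the sponsor does mean both items to be required, the row should say so and the SAP should acknowledge who is thereby excluded.

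Before database lock, compare the investigators' HI-E entries with the Hgb values and transfusion records for every participant with pretreatment Hgb below 11 g/dL. A check limited to those with fewer than 4 transfusions would miss the participant who goes from 6 units to 0 with stable Hgb. Report how many entries depend on the rule chosen.

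The cost is one phrase in two tables and a data review. Scheduled hematology and the transfusions of the 16 weeks before first dose are already collected (protocol Table 8-1), so no new assessment is needed. The documents do not show whether the Hgb that prompted each pre-treatment transfusion is recorded; where it is not, the 9 g/dL condition would need a query to the site.
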